2. BACKGROUND AND RATIONALE

2.1. Epidemiology: Nursing homes (NHs) care for approximately 3 million individuals annually, including 1.5 million frail older persons with advanced chronic disease requiring long-term care, and a growing proportion of seriously ill patients admitted for post-acute care.^{1,2} Approximately 11% of Americans over 85 years reside in NHs. In the past 3 decades, NHs have evolved into complex health care systems serving an increasingly sick and heterogeneous population. While NHs serve a growing number of patients recuperating from acute illnesses, they also are a common site of care for patients nearing the end-of-life. In 2009, 45% of U.S. Medicare beneficiaries who died were in a NH during the last 90 days of life, and 28% died in that setting.³ Taken together, NHs are often charged with guiding patients with complex medical problems and advanced illness through challenging decisions about the direction of their treatment.

2.2. Need to improve advance care planning (ACP) in NHs: Advance care planning (ACP) is a *process* of communication between providers and patients/families to identify anticipated medical decisions and clarify goal-directed treatment preferences. Ideally, ACP leads to completion of *advance directives that come into effect* if/when a patient becomes incapacitated. Advance directives include living wills, appointment of a health care proxy, and formal medical orders to withhold specific treatments, such as resuscitation. In observational studies, ACP is the strongest and most consistent modifiable factor associated with better palliative care outcomes in the NH setting.⁴⁻⁹ The lack of advance directives has been associated with greater use of feeding tubes,^{7, 10, 11} more terminal hospitalizations,^{5, 12-14} higher health care costs,⁹ worse family satisfaction and mental health outcomes,^{6, 10, 15, 16} and lower hospice use.^{10, 17}

The Patient Self-Determination Act (PSDA) of 1991 mandated that NHs ascertain and document patients' advance directives.¹⁸ Unfortunately, advance directive completion remains inadequate and does not always reflect the patient's goals of care.^{4, 6, 8, 18-24} The proportion of NH

patients with DNR orders increased from 31% in 1990 to 52%,¹⁹ but has remained relatively unchanged thereafter.²⁵ Other, perhaps more consequential directives for NH patients, were not influenced by the PSDA and continue to be low. In 2007, only 4% of U.S. NH patients had DNH orders and 11% had orders to withhold tube-feeding.²⁵ Not surprisingly, markers of the quality of end-of-life care, such as terminal hospitalizations, have also not improved.²⁵ Other serious concerns related to advance directives in the NH persist, most notably marked racial and regional disparities,^{8, 26-29} and very low completion rates in post-acute care, where only 32% and 2% of patients have DNR and DNH orders, respectively.²⁹

There have been some, albeit limited, efforts to design and evaluate approaches other than legislation to improve advance directives in NHs.³⁰ An RCT from the late 1990s of an advance directive program in 6 Ontario facilities resulted in more advance directive documentation, fewer hospitalizations, and lower expenditures, with no change in survival.³¹ A more recent initiative is the Physician Order for Life-Sustaining Treatment (POLST) program, which translates treatment preferences into medical orders that are documented on a form designed to be portable across care settings. POLST does not intervene on the process of counseling patients about how to make preference-based decisions. While many states have adopted POLST programs in NHs,³² its efficacy and effectiveness are under-studied. A retrospective cohort study from 90 NHs found that POLST resulted in care consistent directives and greater advance directive documentation.^{33, 34}

There is growing recognition that improving goal-directed care in NHs will require greater focus on improving the *process* of ACP (i.e., helping to prepare patients for medical decision-making), rather than just static advance directive completion.^{18, 35-37} In one of the few rigorous RCTs designed to improve this process, social workers were trained how to have structured ACP discussions with all newly admitted NH patients.³⁸ This approach reduced unwanted care and increased advance directive documentation, but was never adopted into practice perhaps because such complex interventions are resource intensive, require on-going staff training, and are difficult to replicate across facilities.

The proposed pragmatic RCT of the video decision support tools addresses many of the lessons learned, research gaps, and on-going concerns about ACP in NHs by rigorously evaluating the implementation of a standardized, practical intervention that targets the ACP process in two large NH systems.

2.3. Hospitalizations of NH patients are common, burdensome, costly, and often avoidable: An estimated 15% of NH patients are hospitalized in the last week of life.²⁵ Between one-third and one-fifth of patients in sub-acute skilled nursing facilities (SNFs) are re-hospitalized within 30 days.³⁹ Prior work reports that 23-60% of hospitalizations of NH patients are avoidable, either because hospital-level care is unnecessary or unwanted, and, if averted, could potentially save the U.S. health care system billions of dollars annually.⁴⁰⁻⁴⁴

This opportunity and need to reduce avoidable hospitalizations are greatest among patients with advanced chronic illnesses, for whom the burdens of hospitalization often outweigh the benefits. The decision to hospitalize patients should be guided by the primary goal of care (i.e., prolongation of life vs. comfort). The goal of care for many NH patients with advanced disease is comfort. With rare exceptions (e.g., hip fracture), hospitalization seldom promotes a goal of comfort. Hospitalization can be traumatic,^{45, 46} and often involves burdensome and costly treatments that may be of limited clinical benefit.⁴⁵⁻⁴⁸ For example, 68% of feeding tubes are placed in NH residents with advanced dementia during a hospitalization.⁴⁷ Care transitions also place NH residents at risk of medical errors and adverse drug events.^{49, 50} For those NH patients

whose goal of care remains life prolongation, many of the most common illnesses precipitating hospitalization (i.e., infections), can be usually treated with the same efficacy in the NH.⁵¹⁻⁵⁴

Better ACP is a key strategy to reduce avoidable hospitalizations.⁴⁴ A DNH order is the strongest factor associated with lower hospitalization rates.^{5, 12, 55, 56} NHs with higher rates of DNR orders, a marker of facility culture with better ACP, have lower hospitalization rates among dying patients.²⁵ A before and after study of an ACP-focused intervention in SNFs that targeted patients with > 3 hospitalizations in the prior 6 months reduced re-hospitalization rates by 20%.⁵⁷ The Interventions to Reduce Acute Care Transfers (INTERACT) program, of which ACP is a key component, has also been shown to reduce NH hospitalizations.⁵⁸

2.4. Video decision support tools improve ACP for multiple conditions: The traditional approach to ACP primarily relies on ad hoc verbal descriptions of hypothetical clinical states and interventions. This approach is limited because complex scenarios are difficult to envision, provider information is inconsistent, and verbal explanations are hampered by literacy and language barriers. Decision support tools have been used to overcome some of these barriers⁵⁹⁻⁶⁵ and are meant to supplement, not replace, provider counseling by providing standardized information about options and a framework for weighing options with preferences.

More than 700 decision support tools exist, including 50 that utilize videos.⁶³⁻⁶⁵ Video addresses some of the limitations of traditional verbal ACP by providing realistic visual images of complex medical scenarios. A growing body of work, including several RCTs, supports the effectiveness and feasibility of video decision support tools for ACP for various advanced illnesses (e.g., dementia, cancer, heart failure) and among patients in different settings (out-patient, hospital, short-term rehabilitation) (*see Section 3.C.i.c. Preliminary Studies*).⁶⁶⁻⁷⁵ These studies consistently find that subjects who view the video, when compared to those who listen to verbal information, have greater knowledge about their condition and treatment choices and are more likely to choose less aggressive interventions as their preferred care. Findings also show that the videos reduce the racial and health literacy disparities that typically characterize traditional verbal counseling.^{69, 76}

The promise of video for ACP is reflected by the widespread attention this work has received by the scientific community,⁷⁷⁻⁷⁹ media,^{80, 81} the U.S. Congress, and early adoption by major health care systems. Kaiser Permanente, Group Health Cooperative, and the Palo Alto Foundation are currently using the ACP videos in their out-patient and hospital practices. The state of Hawaii is using these tools across health care settings, including NHs (*see Section 3.C.i.d. Preliminary Studies*). However, none of these efforts involve formal research designs or evaluation. Thus, the proposed pragmatic trial is a logical next step towards understanding the real world application of a video ACP support tool for NH patients.

2.5. Electronic health records and secondary data sources are powerful tools for NH health systems research: Since 1998, when The Centers for Medicare & Medicaid Services required full electronic submission of Minimum Data Set (MDS) data, all licensed U.S. NHs have had rudimentary EMRs.^{82, 83} The MDS is a comprehensive, standardized resident assessment instrument federally mandated for use in all licensed U.S. NHs. The latest iteration, the MDS Version 3.0, was introduced in 2010. MDS assessments are completed on all NH patients upon admission, quarterly, annually, and whenever they have a significant status change. The uniformly collected MDS data have been used for care planning, fiscal, policy, and research purposes. Prior work has shown that MDS data are valid and reliable for these purposes as collected in the real world, not merely during field testing.⁸⁴⁻⁹⁰

Over the past 17 years, analyses of the MDS on its own and linked with other secondary data sources, most notably the Medicare and Medicaid claims, have made key contributions to our understanding of clinical outcomes and health care utilization in the NH setting. These merged datasets have been used extensively to address research questions in the areas of ACP and end-of-life care, including: tube-feeding in advanced dementia,^{7, 11, 91, 92} hospitalization,^{5, 8, 39, 93} hospice use,⁹⁴⁻⁹⁶ health care expenditures,⁵⁶ regional disparities,^{11, 92} and prognostication.^{11, 97} Much of this work has emanated from Brown University in efforts led by [name] and in collaboration with [name] (*See Section 3.C.i.a.2. Preliminary Studies*).

The introduction of the MDS stimulated the development of integrated EMR systems in NHs capable of filing MDS assessments, billing payers, and ultimately pharmacy management and physician ordering. One of our partner NH health care systems, Genesis HealthCare, uses PointClickCare™, one of the most sophisticated among these EMR systems.⁹⁸ PointClickCare™ integrates data from MDS assessments, physician order entry, health care utilizations (hospital transfer, hospice referral), and pharmacy prescriptions into patient care plans. Our second partner NH system, PruittHealth, uses American Health Tech,⁹⁹ which has capabilities and components that are very similar to PointClickCare™.

2.6. A pragmatic trial with a cluster randomized design is a well-suited approach to evaluate the effect of the ACP video intervention in NH health care systems: Over the past 15 years, cluster randomized controlled trial (RCT) designs have been increasingly used in health services research, including trials of NH interventions.^{52, 100-108} This work has contributed to more refined and standardized approaches to the unique biostatistical, implementation, and ethical considerations associated with clustered trial designs.^{103, 109-113} Several advantages of cluster RCTs for testing interventions in NHs are notable. Given that the facility is the unit of randomization, the contamination that can occur when randomizing individuals within NHs is avoided. Moreover, the types of interventions being tested will likely be implemented at the NH level. Finally, individual patient consent procedures are often unnecessary provided the study is of low risk.

While the increasing number of cluster RCTs conducted in NHs has established the feasibility of this approach, most were in a relatively small number of facilities and evaluated the effects of interventions under ideal circumstances (i.e., explanatory trials). Pragmatic trials, which intend to determine the effects of interventions under usual conditions, are a next critical translational step in NH research.¹¹⁴ A small but growing number of pragmatic trials of NH interventions have been conducted, all of which were outside the U.S.¹¹⁵⁻¹¹⁷ Based on the 10 domains outlined in the Pragmatic–Explanatory Continuum Indicator Summary Tool (PRECIS),¹¹⁸ the rationale for pragmatic trials in the NH setting is very compelling, particularly for an ACP intervention. NHs must engage all patients in ACP to maintain an expected standard of care and as a matter of federal legislation. However, NH providers include a variety of practitioners caring for a heterogeneous population. Thus, a pragmatic trial that involves facility-wide implementation of a standardized, feasible, but flexible, ACP intervention makes sense. Moreover, large networks of NHs across the U.S. are owned and operated by single corporations, such as Genesis HealthCare and PruittHealth. These NH systems are uniquely suited for pragmatic trials as they have efficient and established infrastructures for staff training and new program implementation. Moreover, they have integrated computerized clinical information systems (e.g., PointClickCare™) providing an easily accessible data source for patient characterization, intervention implementation, and outcomes measurement.

2.7. Summary of background and rationale based on the literature: The significance of the proposed pragmatic cluster RCT of an ACP video intervention in two NH health care systems is summarized in the following points: 1. NHs have evolved into complex health care systems serving an increasingly sick patient population with advanced comorbid conditions; 2. These NH patients often get aggressive and costly interventions that may be of little clinical benefit and inconsistent with their preferences; 3. There is an opportunity to promote more preference-based, higher quality, and cost-effective care among NH patients with advanced disease through better ACP; 4. An intervention comprised of a suite of ACP video decision support tools presents a promising, scalable, and efficacious approach to address that opportunity that can be implemented on a system-wide level in a flexible manner; and, 5. NH systems offer an ideal setting for a pragmatic cluster RCT. This design is enabled by system-wide infrastructures for staff training, program implementation, and existing electronic data capture. Taken together, this work has the potential to improve the quality of care provided to millions of older Americans in NHs and to enable future pragmatic trials in this increasingly important care setting.

3. STUDY DESIGN

This is pragmatic stratified cluster RCT that will evaluate an ACP video support intervention for patients ≥ 65 cared for in 360 NHs (intervention, n=119; control, n=241) within two NH health care systems, Genesis HealthCare and PruittHealth. Aim 1 of this study is to conduct all aspects of this pragmatic trial.

The intervention consists of a suite of five videos designed to assist NH patients with ACP decisions (*see Section 5*). The ACP video intervention will be implemented in NHs assigned to the intervention arm for 24 months. Data needed to assess outcomes will be derived from the NH EMR systems merged with MDS and Medicare files. NHs randomized to the control arm will use the usual ACP procedures practiced in their facilities.

In this stratified cluster RCT, the unit of random assignment is the facility but the unit of analysis is the patient, clustered within the facility (*See Section 4.4.2*). The intervention will be implemented facility-wide, thus all patients cared for in the NHs during the 24-month implementation period are subjects in this study ($N \approx 152,160$). However, our primary outcomes will be measured in targeted sub-populations with advanced comorbid conditions for whom the opportunity and need to improve ACP and goal-directed care are greatest. These subgroups (n~14,760) include very disabled older, long-stay patients with advanced dementia and those with advanced congestive heart failure (CHF) or chronic obstructive pulmonary disease (COPD) (i.e. cardiopulmonary disease).

Outcomes to be compared between patients in the intervention and control NHs include: advance directives orders (DNR, DNH, DNI, and no tube-feeding), hospital transfers, use of other burdensome interventions (new feeding tube insertions, parenteral therapy, intubation, ICU care), hospice use, and Medicare ACP billing codes. The effectiveness of the intervention to improve these outcomes among those targeted sub-populations with advanced illness will be assessed among long-stay (≥ 90 days) NH residents (Aim 2) and new admissions to post-acute care (short-stay < 90 days) (Aim 3). Finally, we will evaluate the effects of the intervention by examining the aforementioned outcomes among long-stay NH patients and new admissions who do NOT have either of the pre-specified advanced illnesses (Aim 4). The primary outcome for this pragmatic trial is hospital transfers (quantified as number of hospital transfers/person-day alive based on Medicare claims data), which include admissions, emergency department visits, and observation stays over a 12-month follow-up period among long-stay residents with advanced dementia and/or advanced

CHF/COPD. Secondary outcomes for these patient groups include advance directive orders, other burdensome treatments, hospice use, and Medicare ACP billing codes.

4. SELECTION AND ENROLLMENT OF PARTICIPANTS

4.1. Facility Inclusion Criteria

Facility eligibility criteria include:

Matched facility ID on Brown University's list of all Medicare/Medicaid-certified nursing facilities in the U.S.

Serve both short and long-stay patients

Have >50 beds

Have an EMR system

Have at least 20 admissions and 20 annual Minimum Data Set (MDS) assessments (regardless of whether patients were discharged alive)

We anticipated that a total of approximately 360 (297 Genesis HealthCare / 63 PruittHealth) facilities would be eligible for random assignment.

4.2. Patient Inclusion Criteria:

As the ACP video intervention will be implemented facility-wide, all patients in eligible NHs during the 24-month implementation period are eligible. There are no exclusions based on age, gender, race, ethnicity, or clinical features.

Although the ACP intervention will be implemented facility-wide, its effectiveness will be examined among targeted NH sub-populations for Aims 2, 3, and 4. Target populations for these Aims include patients ≥ 65 in the NHs during the 24-month implementation period who meet the following eligibility definitions based on MDS assessments. For all three aims, residents will be eligible for the target sub-populations if they meet these criteria either at the start (prevalent cases) or during (incident cases) the 24-month implementation phase. Incident cases include new admissions and long-stay residents who "convert" over the implementation phase by meeting eligibility criteria based upon changes in their repeated MDS assessments.

Aim 2: Patients ≥ 65 who are in nursing home ≥ 90 days (long-stay) who have EITHER of the following two conditions:

1. *Advanced Dementia:* must have all three criteria: a, b, and c
 - a. Alzheimer's disease or other dementia
 - b. Advanced cognitive impairment*
 - c. Extensive or total assistance needed for eating and transferring

*Advanced cognitive impairment is defined as a score of 3 or 4 on the Cognitive Function Scale based on variables from the MDS Version 3.0^{119, 120}

2. *Advanced COPD/CHF:* must have all three criteria: a, b, and c
 - a. CHF/COPD
 - b. Shortness of breath sitting or lying flat
 - c. Extensive or total assistance walking in room, transferring, walking in corridor, locomotion on/off unit, or dressing.

Aim 3: Patients ≥ 65 who are in nursing home < 90 days (short-stay) who have advanced dementia OR advanced CHF/COPD as defined above.

Aim 4: Long and short-stay patients ≥ 65 who do NOT have either advanced dementia OR advanced CHF/COPD as defined above.

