5.2. Intervention Training, Implementation, and Adherence Monitoring

At each intervention facility, two senior staff members were designated as ACP Champions and were responsible for implementing all aspects of the ACP Video Program. Implementation involved two major components: 1. Use of the videos with individual patients and families, and 2. Integration of the ACP Video Program into the workflow of the NH. Our research team provided a standardized approach for both these components through our training program. However, in the spirit of a pragmatic trial, NH staff had the flexibility to tailor aspects of the implementation as dictated by local NH practices, workflow, and culture. Providers also individualized the timing, format, and intensity of ACP Video Program based on each patient's clinical needs.

Intervention training and implementation began in January 2015; approximately 30 intervention NHs were trained in each of 4 sequential waves. The implementation strategy was collaboratively designed by the research team and corporate leaders but executed almost exclusively by the healthcare systems. Each NH designated two ACP program champions, one of whom was a social worker, charged with leading implementation at their facility. Only corporate leaders were aware the intervention NHs were part of an RCT. ACP champions and NH providers were simply told the program was a new, corporate-led initiative.

In keeping with a pragmatic trial, healthcare systems and NHs had flexibility to tailor the implementation protocol to their specific environments. The protocol instructed NH staff to offer videos to patients or families at the following trigger events: 1. Within 7 days of admission or readmission, 2. Every 6 months for long-stay patients, 3. When decisions were being discussed for which there was a specific video (e.g., hospice), and 4. Special circumstances (e.g., out-of-town family visit, change in health status). Clinicians could choose which video(s) to show, with the goal-of-care video being the most widely applicable. Videos were pre-loaded onto tablet devices (two devices per facility) and available for out-of-town family members through a password-protected web link.

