9. STATISTICAL CONSIDERATIONS

9.1. General Design Issues

PROVEN is pragmatic cluster RCT of an ACP Video Program intervention for NH patients cared for in two NH health care systems: Genesis HealthCare and PruittHealth. Rationale for this choice of study design is provided in Section 2.6. The intervention will be implemented facility-wide; thus, all patients in the NHs during the 24-month implementation period comprise the study population. However, the analytic plan focuses on the effect of the ACP Video Program vs. control in the following targeted patient sub-groups:

- Long-stay residents (≥ 90 days) with advanced dementia or advanced CHF/COPD (Aim 2)
- Short-stay patients (< 90 days) with advanced dementia or advanced CHF/COPD (Aim 3)
- Long and short-stay patients without these advanced illnesses (Aim 4).

The primary trial outcome is hospital transfers (number of hospital transfers/person-days alive based on Medicare claims data), which include admissions, emergency department visits, and observation stays over a 12-month follow-up period among Medicare fee-for-service long-stay residents with advanced dementia or advanced CHF/COPD. The primary hypothesis is that the rate of hospital transfers will be lower in the intervention group.

Secondary outcomes include hospital transfer rates in the sub-groups examined in Aims 3 and 4, and the following outcomes for all sub-groups in Aims 2, 3 and 4: advance directives, burdensome treatments, hospice use, and Medicare ACP billing codes.

Each long-stay resident will be followed for up to 12 months starting from the date they are first identified as meeting our target cohort definition during the 24-month intervention period and short-stay patients will be followed for 100 days from their NH admission date. The analytic approach to Aims 2, 3, and 4 are similar. Analyses begin with descriptions of all major variables using frequencies and means/medians with SDs/interquartile ranges, as appropriate. Outcomes will be compared between the control and intervention arms using a zero-inflated Poisson model

with random effects to account for clustering at the NH level. While we do not anticipate an effect on mortality, analyses will also examine the effects on mortality. Primary analyses will follow the intention to treat principle and will adjust for minor imbalances in patient characteristics, as needed.

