9.4. Outcomes

9.4.1. Primary outcome: The primary trial outcome is the hospital transfer rate (number of hospital transfers/person-day alive based on Medicare claims data), which include admissions, emergency department visits, and observation stays) over a 12-month follow-up period among Medicare fee-for-service among long-stay residents with advanced dementia or advanced CHF/COPD over 12 months (Aim 2).

9.4.2. Secondary outcomes: Secondary outcomes include: i. hospital transfer rates in the sub-groups examined in Aims 3 (short-stay patients with advanced dementia or advanced CHF/COPD) and Aim 4 (short-and long stay patients who do NOT have advanced dementia or CHF/COPD), and ii. The following outcomes for target sub-groups defined in Aims 2, 3, and 4: advance directives, burdensome treatments (e.g., tube-feeding), receipt of hospice services, and Medicare ACP billing codes.

All outcomes in the long-stay patient populations are calculated over a 12-month follow-up period. For short-stay patients, advance directive completion rates will be calculated over the admission period, and hospital transfer rates, use of burdensome treatments, and hospice enrollment will be examined within 100-days after the NH admission date.

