Aim 3. To evaluate the effectiveness of the ACP intervention among new admissions to post-acute care with the advanced comorbid conditions: Newly admitted NH patients to post-acute care with advanced dementia or advanced CHF/COPD disease will accrue throughout the 24-month intervention. Measured outcomes for this group will include: advance directives to withhold specific treatments (DNH, DNR, DNI, no tube-feeding) at any time during their post-acute care admission, hospital transfers, and hospice enrollment within 100 days following NH admission. Preliminary data found that 100-day hospital transfer rates among post-acute patients with advanced dementia and/or CHF/COPD was 37%, and that nearly 50% of advanced dementia and 30% of advanced CHF/COPD patients died within 6 months of NH admission. In light of the high mortality rate, we will adopt the hospital transfers per person-day alive approach described for Aim 2 to evaluate the effectiveness of the intervention.

Aim 4. To evaluate the effects of the ACP intervention among long-stay and new admissions to post-acute care WITHOUT advanced dementia or COPD/CHF: The intervention is being implemented facility-wide, thus all long-stay residents and post-acute care admissions will be exposed to it. Aim 4 tests the impact of the intervention on NH patients WITHOUT

$$p(Y_{ij} | X_{ij}) = \begin{cases} \pi_{ij} + (1 - \pi_{ij}) \exp(-\mu_{ij}) & Y_{ij} = 0 \\ (1 - \pi_{ij}) \frac{\exp(-\mu_{ij}) \mu_{ij}^{Y_{ij}}}{Y_{ij}} & Y_{ij} \geq 0 \end{cases}$$

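### Section 4.2 admits prevalent cases for all three aims, which conflicts with the short-stay clock from nursing home admission and with the new-admission definition of the short-stay groups in Aims 3 and 4

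*Combined protocol and SAP*

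**What the plan says.** Section 4.2 (Patient Inclusion Criteria) sets one entry rule for Aims 2, 3 and 4: "For all three aims, residents will be eligible for the target sub-populations if they meet these criteria either at the start (prevalent cases"), or during the 24-month implementation phase (incident cases). New admissions are listed among the incident cases, so a short-stay patient already in the home at the start can enter only as a prevalent case. The Aim 3 population is given as "Patients ≥ 65 who are in nursing home < 90 days (short-stay) who have advanced dementia OR advanced CHF/COPD as defined above", with no condition on the admission date. The Aim 4 definition has none either, and Section 4.3 adds no patient exclusions.

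The clock is set elsewhere. Section 9.1 says that "short-stay patients will be followed for 100 days from their NH admission date". Section 9.4.2 gives the same origin for transfers, burdensome treatments and hospice ("hospice enrollment will be examined within 100-days after the NH admission date"), and for short-stay patients "advance directive completion rates will be calculated over the admission period". Long-stay follow-up instead starts when the resident is first identified as meeting the target definition within the 24-month period (Section 9.1).

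Other sections describe the short-stay groups differently. The précis, the Aim 3 and Aim 4 objectives in Section 1, and Section 3 all speak of new or newly admitted post-acute patients. Section 9.5 says for Aim 3: "Newly admitted NH patients to post-acute care with advanced dementia or advanced CHF/COPD disease will accrue throughout the 24-month intervention".

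**The concern.** The prevalent-case rule suits long-stay residents, whose time zero lies inside the programme period. It does not suit short-stay patients, whose time zero is an admission that may fall up to 89 days before launch. No sentence in the plan drops or truncates that earlier time. Two programmers, one working from Section 4.2 and one from the Aim 3 text in Section 9.5, would build different cohorts.

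Under the 4.2 version, two things happen in Aim 3 and the short-stay part of Aim 4:

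- Transfers, hospice claims and ACP bills from before the programme existed count as outcomes. The hospice exclusion in Section 1 does not prevent this. It applies at the start of observation, which for these patients is admission, so hospice enrolment between admission and launch still counts.
- A prevalent patient must be alive and in the home at launch. The pre-start days therefore contain no deaths and no transfers that ended the stay (left truncation).

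At stake are H3b, H3c, the short-stay parts of H4b and H4c, and the ACP billing comparison, all of which are secondary.

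**Working it through.** The plan states no figure on this point, so there is none to reproduce. The 103 facilities per arm in Section 9.2 concern the long-stay primary outcome and do not depend on it.

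**Step 1: follow one patient through the text.** Take a short-stay patient who meets the Aim 3 criteria, was admitted 30 days before launch and is still in the home at launch.

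- Section 4.2: eligible, as a prevalent case.
- Sections 9.1 and 9.4.2: the 100 days run from admission, so days 1 to 30 are before the programme and days 31 to 100 are within it.
- Section 9.5, Aim 3: not a patient who accrued during the intervention, so not in the cohort.

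The passages give different answers for the same patient.

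**Step 2: how many such patients, and how much time.** From the documents: a 24-month period (taken as 730 days), short stay under 90 days, and a 100-day window. Assumed, because the documents give no value: length of stay L, steady admissions, and a full 100-day window for everyone.

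Patients in the home at launch are those admitted in the preceding L days, so

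- prevalent share = L / (730 + L)
- mean pre-start time = L / 2
- pre-start share of all 100-day windows = [L / (730 + L)] × (L / 2) / 100

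Example, L = 30: 30/760 = 3.9%; 30/2 = 15 days; 3.95% × 0.15 = 0.6%.

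| Assumed stay (days) | Prevalent share of cohort | Mean pre-start days | Pre-start share of windows |
|---|---|---|---|
| 15 | 2.0% | 7.5 | 0.15% |
| 30 | 3.9% | 15 | 0.6% |
| 45 | 5.8% | 22.5 | 1.3% |
| 60 | 7.6% | 30 | 2.3% |
| 89 | 10.9% | 44.5 | 4.8% |

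**Step 3: variable stays.** Simulated exponential stays cut off at 90 days, with means of 20, 30 and 45 days before the cut, give prevalent shares of 2.5%, 3.3% and 4.1%, mean pre-start times of 17.6, 21.6 and 24.4 days, and pre-start shares of 0.4%, 0.7% and 1.0%. These lie inside the range in the table.

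**Step 4: direction.** The same entry rule and clock apply in both arms. Before launch the arms do not differ in programme exposure, so pre-start time adds observation with no expected difference. That pulls a real effect slightly towards zero and creates no evident bias when there is none. The net effect on the transfer rate itself is not derived: some pre-start transfers are added, and others are missing because patients whose stays ended before launch never enter.

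**The case against.** The strongest reply is that the documents largely answer the question. The précis, the Section 1 objectives, Section 3 and Section 9.5 all call the short-stay groups new admissions. On that reading there are no short-stay prevalent cases, and a clock from admission is correct. This carries weight: a reader might infer from 4.2 that pre-programme events are settled trial outcomes, and the documents do not support that. It does not remove the conflict, because 4.2 is the operative eligibility text, it names all three aims, and the term new admission is nowhere tied to the start date. The accrual sentence in 9.5 covers Aim 3; Aim 4 has no equivalent for its short-stay part.

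Three further objections stand and limit the point:

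- **Prevalent patients are not empty observations.** With the simulated stays, about 76 to 82 of their 100 days fall after launch (100 − 24.4 to 100 − 17.6).
- **They can still be offered a video.** Many will be past the admission trigger ("Within 7 days of admission or readmission"), and the six-monthly trigger is for long-stay patients. But Section 5.2 also calls for an offer on a change in clinical status, when a decision arises that has its own video, in special circumstances, and on readmission. It would be wrong to infer that these patients are beyond the programme's reach.
- **Advance directives are not a special case.** Section 1 measures the last observed status, so orders that predate the programme count in every cohort, including new admissions who arrive with one.

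**Conclusion.** The point holds as a conflict between the entry rule in Section 4.2 and both the short-stay clock and the new-admission wording for Aims 3 and 4. It should be settled before the cohorts are built. If 4.2 is followed, the consequence is a small left-truncation problem and a mild dilution in secondary outcomes. The size, 2.0% to 10.9% of short-stay patients and 0.15% to 4.8% of their 100-day windows, rests wholly on assumed stays of 15 to 89 days and steady admissions.

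A reader might go further and infer that short-stay rates per day alive are understated in both arms. The documents supply no transfer or death rates by day since admission from which to derive that, and the two mechanisms act in opposite directions on the count of transfers. Nor does anything here reach the primary outcome: long-stay follow-up in Aim 2 starts at identification within the 24-month period.

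**What to change.** In Section 4.2, limit prevalent cases to long-stay residents (Aim 2 and the long-stay part of Aim 4). For Aim 3 and the short-stay part of Aim 4, include only patients whose nursing home admission date is on or after the start of the 24-month period. The 100-day clock from admission can then stay as it is, and pre-programme time in these cohorts falls to zero.

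The same sentence should define the start date for every facility. Section 5.2 describes training and implementation in four sequential waves, and the text assigns no start date to control homes. The definition must work the same way in both arms, or the date filter would itself select different calendar periods.

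The cost is one or two sentences and a date filter in the cohort program. The filter removes the prevalent short-stay patients, a few percent of the cohort at most of the assumed stays and about 11% at the 89-day extreme. These patients carry partial information, so a little precision is lost in the secondary analyses.
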